#### 8.3.3 Supportive Analysis of the HDSM-Ax-7 Co-Primary Endpoint

As a supportive analysis of the HDSM-Ax-7 co-primary endpoint, change from baseline to EOT will be analyzed as a continuous measure. The analysis model will be an ANCOVA model with treatment, baseline HDSM-Ax-7 score, and analysis center as covariates. The estimand for this analysis is the difference in mean baseline to EOT changes in HDSMAx-7 total scores between sofpironium bromide gel, 15%, and vehicle arms among all ITT subjects, regardless of treatment adherence.

#### 8.3.4 Supportive Analysis of the GSP Co-Primary Endpoint

Two supportive analyses will be performed for the GSP co-primary endpoint:

(1) If the Shapiro-Wilk test for Normality of the GSP baseline to EOT data is violated, then, using the same methodology as described in Section 8.3.2, an ANCOVA analysis will be performed for the non-rank-transformed, continuous GSP data. The model will use the fixed effects of treatment, baseline GSP, and analysis center. If the Shapiro-Wilk test for Normality of the GSP baseline to EOT data is not violated and the continuous GSP is used for the co-primary endpoint, then the ranked GSP ANCOVA analysis will be performed as a supportive analysis.

(2) To further address the potential large variations in GSP data, mixed model repeated measures (MMRM) analyses will be performed to estimate the average sofpironium bromide gel, 15% treatment effect over the 6 week course of treatment, i.e. the average sofpironium bromide gel, 15% versus vehicle difference from baseline to Days 8, 15, 22, 29, 36, and EOT, using both rank-based and non-rank-based data. As the MMRM methodology is known to be robust to missing data, missing data will not be imputed for this analysis.

The model specified is a REML-based analysis with an identity link.

The following fixed effects are planned:

- Treatment (class effect: sofpironium bromide gel, 15% group, vehicle)
- Visit (visits will be coded as ordinal, where Visit 5 = 1, Visit 6 = 2, Visit 7 = 3, Visit 8 = 4, Visit 9 = 5, EOT = 6)
- Baseline GSP (ranked or non-ranked, depending on the model)
- Analysis center
- Baseline-by-visit interactions
- Treatment-by-visit interactions

Based on the Study BBI-4000 CL-203 results, significant treatment versus visit interactions are not expected. Nevertheless, should treatment versus visit interactions be significant (i.e. p<0.05), the estimated treatment effect at EOT will be reported. An unstructured correlation matrix will be used to model the variance and covariance of within-subject repeated measures and restricted maximum likelihood estimation. The

Kenward-Roger method will be used for the denominator degrees of freedom. In order to arrive at the correct structure for the data, if the model fails to converge using an unstructured covariance matrix, other covariance structures will be tested as follows: heterogeneous Toeplitz (TOEPH), heterogeneous AR(1) (ARH1), heterogeneous compound symmetry (CSH), Toeplitz (TOEP), spatial power with numeric visit number SP(POW)(VISn), autoregressive (1) (AR(1)), and compound symmetry (CS). The model that converges with the lowest Akaike Information Criterion (AIC) will be used. If the treatment-by-visit interactions are not significant overall, they will be removed from the final model; similarly for the baseline-by-visit interactions.

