Overall, all three sofpironium bromide gel concentrations, 5%, 10%, and 15%, have exhibited a larger absolute mean reduction in gravimetric sweat production (GSP) from baseline to end of treatment (EOT) compared with vehicle. Better improvement in GSP response was associated with higher concentrations of sofpironium bromide. However, while there was a slight trend toward dose response, all gel concentrations were essentially equivalent in patient-reported outcome measures based on the Hyperhidrosis Disease Severity Measure-Axillary (HDSM-Ax), Dermatology Quality of Life Index (DLQI), and Hyperhidrosis Disease Severity Score (HDSS), suggesting that all three concentrations are efficacious. The response was seen as early as Day 8 and remained consistent throughout the applicable treatment period.

Clinical Pharmacokinetics Conclusions

In PK studies conducted to date, both sofpironium and its major metabolite BBI-4010 could be measured in the majority of subjects. Systemic exposure to sofpironium and BBI-4010 appeared to increase in an approximately dose-proportional manner when comparing the 5% and 15% gel concentrations, indicating that applying a more concentrated gel increased exposure. However, inter-subject variability of PK parameters was extremely high. Absorption is thought to be affected by skin thickness, temperature, hydration, and degree of occlusion.

Systemic exposure of sofpironium and BBI-4010 was typically minimal following the first dose (Day 1) and also after multiple doses (Day 21). Sofpironium accumulation after Day 1 was not observed. Plasma concentrations of BBI-4010 appeared to be lower than those of sofpironium. Steady state is likely reached within the first 24 hours. In general, plasma concentrations of sofpironium and BBI-4010 showed most samples analyzed were below 1 ng/mL, with many below the lower limit of quantification of 0.05 ng/mL for both sofpironium and BBI-4010.

Risk to Subjects

As an anticholinergic drug, administration of sofpironium bromide gel could be associated with signs or symptoms typical of anticholinergic effect such as dry mouth, blurred vision, dizziness, constipation, urinary retention, or tachycardia. The previous sofpironium bromide exposure to humans has demonstrated a low incidence of these effects, which are generally mild in severity. All such effects have been observed, and as expected, to be transient.

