Analysis Model: ANCOVA model (either non-ranked or ranked, pending outcome of normality test)

Fixed effects: The following fixed effects are planned:

- Treatment (class effect: sofpironium bromide gel, 15% group, vehicle group)
- Baseline GSP (either non-ranked or ranked, pending outcome of normality test)
- Analysis center (see Section 10.3.3)

Hypothesis Tested:

The null hypothesis

H₀: The rank-based GSP changes from baseline to EOT are the same in the sofpironium bromide gel, 15%, and vehicle groups

will be tested against the two-sided alternative hypothesis:

H₁: The rank-based GSP changes from baseline to EOT are not the same in the sofpironium bromide gel, 15%, and vehicle groups.

Estimand: The estimand of this co-primary efficacy analysis is the mean difference between treatments, sofpironium bromide gel, 15%, versus vehicle, in the change from baseline to EOT for GSP among all ITT subjects, regardless of treatment adherence.

Additionally, the following secondary and supportive analyses will be performed for the GSP co-primary endpoint:

- (a) Using the same methodology as described above, an ANCOVA analysis will be performed foreither the non-rank transformed, continuous GSP data, or the rank transformed GSP data, pending the results of the normality test. If the normality assumption is violated and the rank-transformed data are used as the co-primary endpoint, analysis of the continuous data will be supportive. If the normality assumption holds and the continuous data are used as the co-primary endpoint, then analysis of the rank-transformed data will be supportive.
- (b) To further address the potential large variations in GSP data, mixed model repeated measures (MMRM) analyses will be performed to estimate the average sofpironium bromide gel, 15% treatment effect over the 6-week course of treatment, i.e. the average sofpironium bromide gel, 15% versus vehicle difference from

A a tha MMDM

baseline to Days 8, 15, 22, 29, 36, and EOT, using both rank-based and non-rank-based data. As the MMRM methodology is known to be robust to missing data, missing data will not be imputed for this analysis. In addition, based on the BBI-4000 CL-203 results, treatment versus visit interactions are not expected. Details of the analysis models will be provided in the SAP.

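### The supportive GSP repeated-measures analysis promises a six-week average effect, but an interaction test at p<0.05 decides what is reported

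*SAP*

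**What the plan says.** SAP 8.3.4(2) gives the MMRM one purpose: "to estimate the average sofpironium bromide gel, 15% treatment effect over the 6 week course of treatment". It spells this out as "the average sofpironium bromide gel, 15% versus vehicle difference from baseline to Days 8, 15, 22, 29, 36, and EOT", on both ranked and non-ranked data. The starting model has treatment, visit, baseline, analysis center, baseline-by-visit and treatment-by-visit terms, with an unstructured covariance as first choice.

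Two data-dependent rules follow:

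- Interaction significant: "should treatment versus visit interactions be significant (i.e. p<0.05), the estimated treatment effect at EOT will be reported".
- Interaction not significant: "If the treatment-by-visit interactions are not significant overall, they will be removed from the final model". The baseline-by-visit terms are treated the same way.

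The SAP expects the second branch: "Based on the Study BBI-4000 CL-203 results, significant treatment versus visit interactions are not expected". Protocol 10.3.2(b) states the same aim, contains no switching rule, and leaves the model to the SAP ("treatment versus visit interactions are not expected. Details of the analysis models will be provided in the SAP"). Neither document defines the contrast or the visit weights that make up the average.

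**The concern.** The stated target is a single quantity, but one test on the trial data chooses both the fitted model and, on one reading, the quantity reported. When the effect changes over time, the six-week average and the EOT effect differ and the test is most likely to reject. On that reading the average is given up in just the situation where it carries separate information. The EOT estimate is then reported only when the visits appear to differ, and its confidence interval takes no account of that selection.

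The SAP list of planned tables runs this analysis four times: ranked and continuous, each in the ITT and mITT populations. The interaction test could fall differently across the four, so tables with parallel titles could report different quantities.

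**Working it through.** **The plan's own figure.** The documents give no figure for the MMRM. The nearest is the GSP sample size in SAP 2.6: difference 16.6 in mean ranks, SD 39.5, two-sided alpha 0.05, power 0.95. Per arm, n = 2 × (1.960 + 1.645)² × (39.5/16.6)² = 147.2, rounded up to 148, or 296 in total. This matches the SAP. The non-ranked inputs, 73 mg and SD 170, give 141 per arm and set the scale below.

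**Branch 1: interaction dropped.** With a common treatment effect, the estimate weights visits by w = V⁻¹1 / (1′V⁻¹1), where V is the covariance across the six time points. EOT is the median of three visits (SAP 8.1.1); each of the other five is a single reading. Assume exchangeable visits with correlation ρ and normal errors. The median of three independent normal errors has 0.449 of the variance of one, so V = ρ11′ + (1−ρ)·diag(1,1,1,1,1,0.449). The weights are then proportional to 1 for each single visit and 1/0.449 = 2.23 for EOT, whatever ρ is:

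- EOT: 2.23/7.23 = 0.31
- each other visit: 1/7.23 = 0.14

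Equal weighting would be 1/6 = 0.167 each. The gap from the equal-weight average is (0.308 − 0.167) × (EOT effect − mean effect at the other five visits). For the assumed profiles used below:

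- flat 73 mg: 0
- rising 53 to 73 (average 67.0, other visits 65.8): 0.142 × 7.2 = 1.0 mg
- rising 30 to 73 (average 53.8, other visits 50.0): 0.142 × 23.0 = 3.3 mg
- rising 13 to 73 (average 43.0, other visits 37.0): 0.142 × 36 = 5.1 mg
- waning 103 to 73 (average 88.0, other visits 91.0): 0.142 × (−18) = −2.6 mg

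Under AR(1) with correlation 0.3 to 0.7, the first and last time points get 0.21 to 0.31 each. Under compound symmetry with equal variances, the weights are equal.

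**Branch 2: EOT reported.** The whole rule was simulated, reading the EOT effect as a replacement for the average. Settings: 150 per arm, six time points, complete data, SD 170 mg, unstructured covariance, a 5-df Hotelling test of the interaction, and 4,000 runs per scenario. Assumed: correlations 0.3, 0.5 and 0.7; compound symmetry, AR(1) or the median-of-three pattern; and the time profiles. Ranges are over the covariances.

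| Effect over visits (mg) | True average | Interaction significant | Mean reported | Coverage of the average |
|---|---|---|---|---|
| Flat 73 | 73.0 | 4.6-5.4% | 72.8-73.6 | 93.2-94.7% |
| 53 to 73 | 67.0 | 8-22% | 67.2-69.7 | 92.7-94.4% |
| 103 to 73 | 88.0 | 11-46% | 77.7-84.7 | 89-92% |
| 30 to 73 | 53.8 | 21-80% | 59.9-71.0 | 83.5-87.8% |
| 13 to 73 | 43.0 | 36-99% | 57.7-72.7 | 67-76% |

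Splitting the 30-to-73 case shows where the loss arises. When the interaction is not significant, the mean reported is 52.8-57.7 with coverage 93.7-95.1%. When it is significant, the mean reported is 74-85: a different quantity, and on average above even the true EOT effect of 73.

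**Alternative.** With the interactions kept and a 1/6-each contrast, the mean was within about 1 mg of the true average in every scenario, and coverage was 94.0-95.7%.

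**The case against.** The strongest reply has four parts.

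- **Expected profile.** The sponsor expects the non-significant branch, and Protocol section 1 says of earlier studies: "The response was seen as early as Day 8 and remained consistent throughout the applicable treatment period". The steep ramps sit badly with that. This stands: if the effect is flat, the rule does almost no harm.
- **Wording.** The SAP says that the EOT effect is reported, not that the average is withheld. This also stands: a reader might infer that the SAP abandons the average, but the text allows EOT in addition. The coverage losses apply only to the replacement reading, and the SAP needs to say which is meant.
- **Information available elsewhere.** By-visit ANCOVAs of ranked and absolute GSP change are planned as exploratory analyses, and the EOT comparison is the co-primary analysis itself. The time profile and EOT effect will therefore be visible. None of these supplies the six-visit average, which is the stated reason for the MMRM.
- **Weights.** Precision weighting is a legitimate choice when the effect is constant. This stands.

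A reader might go further and infer that dropping the interaction means the analysis does not estimate the six-week average, with EOT dominating. The documents do not support that. EOT weights as high as 1.19 appear only if a correlation of 0.8 is paired with an EOT SD 0.75 of a single visit's. Under the exchangeable median-of-three model, the SD ratio at correlation 0.8 is √(0.8 + 0.449 × 0.2) = 0.94, and the EOT weight stays at 0.31.

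**Conclusion.** The point holds in a limited form. The SAP names one estimand, defines no contrast for it, and lets an interaction p-value steer what is reported. The consequential part is the switch to EOT. If EOT replaces the average, coverage of the six-week average is close to nominal for a flat or mildly rising effect, 89-92% for the waning profile and 84-88% for the 30-to-73 mg ramp; it is lower still for a steeper ramp that earlier data make unlikely. Removing a non-significant interaction is the lesser matter, worth at most about 5 mg in the scenarios tried and nothing if the effect is constant.

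These sizes rest on assumed correlations, covariance patterns and time profiles, complete data and the mg scale; the rank-based version was not simulated. The analysis is supportive and lies outside the gated sequence of SAP 8.2.4, so the co-primary tests, alpha and sample size are untouched. Correcting it is desirable, not essential.

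**What to change.** Amend SAP 8.3.4(2) as follows:

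- Keep the treatment-by-visit and baseline-by-visit terms whatever their p-values.
- Define the MMRM result as the equal-weight LS-mean contrast, 1/6 on each of Days 8, 15, 22, 29, 36 and EOT, for ranked and non-ranked data.
- Report the EOT and visit-specific differences beside it in every case.
- Give the interaction p-value as description only, with no effect on the model or on what is reported.

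The cost is a few lines of SAP wording and one ESTIMATE statement, with no new data. The statistical price is a slightly wider interval when the effect really is constant. Under the median-of-three model at correlation 0.5, the variance factors are 0.5 + 0.5 × (5 + 0.449)/36 = 0.576 for equal weights and 0.5 + 0.5/7.23 = 0.569 for precision weights, so the standard error rises by about 0.6%. Under AR(1) with correlation 0.7, applying the same weight formula gives about 3%.

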#### 8.3.5 Sensitivity Analyses of the Co-Primary Efficacy Endpoints

As stated in Section 8.2.1.1, multiple imputations procedures for missing HDSM-Ax-7 and GSP values will be performed prior to the co-primary efficacy analyses under MAR and MNAR assumptions. In order to support the results of the co-primary GSP analysis, the ranked GSP and non-rank-transformed GSP ANCOVA analyses will be repeated without imputing missing data, and again after removing outlier data. To further explore the robustness of the primary analysis results to different missing data assumptions, analyses using two additional imputation methods will be performed as presented below. The first is an analysis of the HDSM-AX-7 co-primary endpoint with missing data imputed as failure/non-response. The second is a tipping point analysis on both coprimary endpoints, using multiple imputations for missing data. Additionally, the 7 items in the HDSM-Ax-7 scale will be analyzed individually to support the primary analysis for this co-primary endpoint. The below sensitivity analyses will be performed using the ITT Population and the mITT Population.

| Table | 8-2 | Summary of Sensitivity Analyses of the Co-Primary Efficacy |
|-------|-----|--|
|       |     | Endpoints  |

| Sensitivity
Analysis
Number | Co-Primary
Efficacy
Outcome
Assessed | Sensitivity Analysis   | Populations |
|-----------------------------------|---|--|-------------|
| 1                                 | GSP change from
baseline to EOT            | Analysis performed on
available data only without
imputing missing data;
using both ranked and non-
ranked data. | ITT, mITT   |

| 2 | GSP change from
baseline to EOT   | Subjects with outlying data
removed from analysis;
using both ranked and non-
ranked data (multiple
imputations for missing
data). | ITT, mITT |
|---|--|---|-----------|
| 3 | HDSM-Ax-7 2-
point
improvement from
baseline to EOT                   | Missing data imputed as
failure/non-response (single
imputation only)   | ITT, mITT |
| 4 | HDSM-Ax-7 2-
point
improvement and
GSP change from
baseline to EOT | Tipping point analysis
(multiple imputations for
missing data)  | ITT, mITT |
| 5 | HDSM-Ax-7 2-
point
improvement from
baseline to EOT                   | Analysis of the influence of
the 7 individual items in the
HDSM-Ax-7 scale (multiple
imputations for missing
data)                    | ITT, mITT |

# 8.3.5.1 Sensitivity Analysis 1: GSP, All Available Data, no Imputations

To further investigate the robustness of the GSP co-primary efficacy endpoint, the ranked and non-rank-transformed GSP analyses will be repeated on all available data only without imputing missing data. The exact same analysis models (ANCOVA) will be used on the observed ranked and non-ranked change in GSP from baseline to EOT.

#### 8.3.5.2 Sensitivity Analysis 2: GSP, Outlying Data Removed, Multiple Imputations

To further investigate the robustness of the GSP co-primary efficacy outcome, the ranked and non-rank-transformed GSP analyses will be repeated with outlier data (as defined in

Section 8.2.1.2) removed from the analysis data set (both sofpironium bromide gel, 15% group and vehicle group) before any endpoint analysis is performed. The methodology will be similar to the primary analysis of the GSP co-primary endpoint. For missing data imputation purposes, outlier data will also be removed from the imputation sampling database. The exact same analysis models (ANCOVA) will be used on the observed ranked and non-ranked change in GSP from baseline to EOT. This differs from the analysis of the GSP co-primary endpoint, in that outlier GSP data is kept in the primary analysis but removed for this sensitivity analysis.

# 8.3.5.3 Sensitivity Analysis 3: HDSM-Ax-7, Missing Data imputed to Failure/Non-Response

In this analysis, missing EOT HDSM-Ax-7 cases will be analyzed as failure/nonresponder in both treatment groups. The same co-primary HDSM-Ax-7 logistic regression model will be re-run on the HDSM-Ax dataset subjects with missing data modelled as not having improved by at least 2 points. The treatment success proportions estimates will also be reported.

#### 8.3.5.4 Sensitivity Analysis 4: HDSM-Ax-7 and GSP, Tipping Point Analysis

A tipping point analysis will be conducted to investigate what type of missing data would cause a positive between-arm comparison of the outcomes of the co-primary efficacy endpoints to be non-significant. These analyses will be conducted separately for the HDSM-Ax-7 and GSP co-primary endpoints.

For the GSP co-primary endpoint, missing data in the vehicle arm will be assumed to be MAR, while missing data from the sofpironium bromide gel, 15% arm will be imputed assuming that subjects with missing data have missing GSP data that are worse by a prespecified  $\Delta$  compared to similar subjects with observed data. Missing values will be multiply imputed via this method with increasing  $\Delta$  values. A  $\Delta$  increment of 5 mg will be used for this study. The GSP co-primary efficacy outcome analysis methodology will be applied to the imputed datasets and repeated until statistical significance no longer holds. The tipping point at which the results are no longer significant will be identified and the results will be summarized graphically.

For the HDSM-Ax-7 co-primary endpoint, identical imputation methodology to that described above for the GSP will be applied to the HDSM-Ax-7 total scores, and the resulting values will be dichotomized into responders using the 2-point improvement criteria. A  $\Delta$  increment of 0.5 (in a 0-4 scale) will be used for this study. The HDSM-Ax-7 co-primary efficacy outcome analysis methodology will be applied to the imputed datasets and repeated until statistical significance no longer holds. The tipping point at which the results are no longer significant will be identified and the results will be summarized graphically.

#### 8.3.5.5 Sensitivity Analysis 5: Analysis of the Influence of 7 individual items in the HDSM-Ax-7 scale

Sensitivity analyses will be conducted on the missing data imputed ITT Population to investigate whether any of the individual items in the HDSM-Ax-7 scale are overly influencing changes observed in the total score. First, a subject will be counted as a responder if they achieve at least a 2-point improvement in the individual question from baseline to EOT. The logistic regression model for the primary analysis for HDSM-Ax-7 will be repeated for each of the 7 individual items, and each individual question will be analyzed separately. Secondly, one of the 7 items will be omitted, and the HDSM-Ax-7 total score will be calculated as the average of the remaining 6 items. The primary logistic regression analysis for 2-point improvement response rate will be performed on this 6-item scale. This process will be repeated 7 times, each time with a different item of the HDSM-Ax-7 scale removed from calculation of the overall score.

## 8.3.6 Secondary Efficacy Analyses

The three secondary efficacy endpoints are described in Section 8.1.3.

If both co-primary analyses yield statistically significant results in favor of the sofpironium bromide gel, 15% group, the three secondary efficacy endpoints will be tested in the ITT population in a fixed sequence in the order presented in Section 8.1.3. Testing will continue only if all previously tested null hypotheses have been rejected at the 2-sided alpha < 0.05 significance level in favor of sofpironium bromide gel, 15%.

The analysis of the three responder secondary endpoints specified in Section 8.1.3 will be conducted using the same logistic regression model as that used for the HDSM-Ax-7 coprimary efficacy analysis. For each model, the covariates include treatment, baseline parameter score, and analysis center. For the composite endpoints, both HDSM-Ax-7 baseline and GSP baseline will be included as covariates.

